9.3 Time to Response

Time to response (TTR) is only defined for subjects whose best overall response are CR or PR. Time to response is defined as the time from the date of first dose to the date when CR or PR is observed, whichever is earlier. TTR will be listed but not summarized unless there is a sufficient number of subjects who achieve ORR. In such case, TTR will be summarized using descriptive statistics. TTR will also be summarized similarly based on the irRC.

9.4 Duration of Response and Clinical Benefit

Duration of response (DOR) is only defined for subjects whose best overall response is CR or PR. The duration of response is the time between the first CR or PR, whichever is earlier, to progressive disease or death, whichever is earlier. DOR is subject to the censoring rules as given in Table 1. DOR will be listed but not summarized unless there is a sufficient number of subjects who achieve ORR. In such case, DOR will be summarized using the Kaplan-Meier method with number and percentage of subjects who have events or censored, the quartiles (25%, median, and 75%) and 95% confidence interval for the median.

Duration of clinical benefit (DCB) is only defined for subjects whose best overall response are CR, PR, or SD. The duration of clinical benefit is the time between the first CR, PR, or SD whichever is earlier, to progressive disease or death, whichever is earlier. DCB is subject to the censoring rules as given in Table 1. DCB will be listed but not summarized unless there is a sufficient number of subjects who achieve ORR. In such case, DCB will be summarized using the Kaplan-Meier method with number and percentage of subjects who have events or censored, the quartiles (25%, median, and 75%) and 95% confidence interval for the median.

[REDACTED]

[REDACTED]

[REDACTED]	[REDACTED]	[REDACTED]
[REDACTED]	[REDACTED]	[REDACTED]
[REDACTED]	[REDACTED]	[REDACTED]
[REDACTED]	[REDACTED]	[REDACTED]

[REDACTED]	[REDACTED]	[REDACTED]
[REDACTED]	[REDACTED]	[REDACTED]
[REDACTED]	[REDACTED]	[REDACTED]
[REDACTED]	[REDACTED]	[REDACTED]
[REDACTED]	[REDACTED]	[REDACTED]

[REDACTED]

[REDACTED]

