### 10.5.3 Efficacy

The efficacy outcomes will include:

1. objective response rate (ORR)
2. best overall response (BOR)

■ [REDACTED]

4. duration of response (DOR)

5. clinical benefit rate (CBR)

6. time to response (TTR)

■ [REDACTED]

The primary efficacy measurement will be ORR per RECIST v1.1 based on the Response Evaluable population by tumor type. The number and proportion of subjects with objective tumor response (CR and PR) will be calculated based on number of subjects with measurable disease at baseline. Ninety-five percent (95%) confidence interval (CI) will also be calculated using exact binomial method. Data listing for tumor assessments and tumor response will be provided.

A secondary measurement will be BOR per RECIST v1.1 based on the Response Evaluable population by tumor type. The number and proportion of subjects with a best overall response of CR or PR will be calculated based on number of subjects with measurable disease at baseline. Ninety-five percent (95%) CI will also be calculated using exact binomial method.

DOR will be defined as the time from first documented CR or PR until the earliest evidence of disease progression, new subsequent anti-cancer therapy, or death from any cause. DOR will be estimated using Kaplan-Meier method for those subjects who have a CR or PR.

Clinical benefit rate will be calculated as the number of subjects with confirmed CR, PR, or SD (where the duration of SD should be  $\geq 3$  months) divided by the total number of subjects in the Response Evaluable Population. The number and proportion of subjects with clinical benefit will be summarized.

The time to response will be summarized descriptively for subjects who have a CR or PR.

[REDACTED]

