5 GENERAL ANALYSIS CONSIDERATIONS AND DEFINITIONS

The statistical analyses will be reported using summary tables, figures, and data listings. Unless otherwise specified, data collected during the dose escalation phase will be presented by dose cohort and overall. Data collected during the dose expansion phase will be presented by tumor type and overall.

Summary statistics for continuous variables will include the mean, standard deviation, median, minimum, and maximum. The mean will be presented to one decimal place beyond which the data were captured. The standard deviation will be presented to two decimal places beyond which the data were captured. The minimum and maximum will be presented to the precision with which the data were captured.

Categorical variables will be presented as frequency counts and percentages. A row or column denoted 'Missing' will be included in count tabulations where necessary to account for dropouts and missing values. Percentages will be rounded to 1 decimal place and the percent will be suppressed when the count is zero. The denominator will be the number of subjects in that dose cohort within the population of interest unless otherwise noted.

Time-to-event variables will be analyzed using the Kaplan-Meier method. The number and percentage of subjects with events or censored will be presented. The Kaplan-Meier estimates for quartiles (i.e., 25%, median, and 75%) and the 95% confidence interval for the median will be presented. All time to event variables will be plotted using the Kaplan-Meier method.

All data, including data collected from the electronic case report form (eCRF) and derived for statistical analysis, will be listed.

Cycle 1/Day 1 (C1D1) is defined as the first day of study treatment administration. Other study days will be calculated as follows:

- for any date post the date of C1D1:
Study day = visit date – date of C1D1 + 1
- for any date prior to the date of Cycle 1/Day 1:
Study day = visit date – date of C1D1

Unless otherwise specified, the baseline is defined as the last non-missing value prior to C1D1.

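### The summary of duration of clinical benefit depends on a count of responders that leaves out stable disease, and the DOR and TTR summaries are conditional in the SAP but not in the protocol

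*SAP*

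**What the plan says.** **DCB.** SAP 9.4 sets the population: "Duration of clinical benefit (DCB) is only defined for subjects whose best overall response are CR, PR, or SD". It sets the clock: "The duration of clinical benefit is the time between the first CR, PR, or SD whichever is earlier, to progressive disease or death". It then sets the condition for a summary: "DCB will be listed but not summarized unless there is a sufficient number of subjects who achieve ORR". SAP 9.2 defines ORR as the proportion with confirmed CR or PR as best response.

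**DOR and TTR in the SAP.** SAP 9.4 says "DOR will be listed but not summarized unless there is a sufficient number of subjects who achieve ORR", and SAP 9.3 says "TTR will be listed but not summarized unless there is a sufficient number of subjects who achieve ORR". None of the three sentences gives a number.

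**DOR and TTR in the protocol.** Protocol 10.5.3 says "DOR will be estimated using Kaplan-Meier method for those subjects who have a CR or PR" and "The time to response will be summarized descriptively for subjects who have a CR or PR". Neither sentence has a minimum.

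**General rules in the SAP.** Section 5 says "Time-to-event variables will be analyzed using the Kaplan-Meier method" and adds that all such variables will be plotted, again with no minimum. Section 14 states that no changes from the protocol's analyses are planned. Section 9 keeps an unconditional listing of tumor response and time-to-event data by subject.

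**The concern.** DCB covers responders and stable subjects, but the decision to summarise it rests on responders alone. The condition is worded as it is for DOR, where it at least counts the right subjects. For DCB it could withhold the summary when there are few responders and many stable subjects, which is when DCB says most beyond DOR.

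DOR and TTR are secondary objectives. The SAP makes their summaries depend on an unstated count and does not declare this as a change. In an open-label trial, an undefined minimum leaves the choice to summarise or not until responses are already known. A plan should not leave that open, even when all analyses are descriptive.

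**Working it through.** The plan gives no figure to reproduce: there is no stated minimum and no power basis for the sample size. The check is a comparison of the texts, then two illustrations of scale.

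**1. The texts side by side**

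| Endpoint | Defined for | SAP summary depends on | Protocol 10.5.3 |
|---|---|---|---|
| DCB | CR, PR or SD | unstated number of responders | not in the readable text |
| DOR | CR or PR | unstated number of responders | Kaplan-Meier, unconditional |
| TTR | CR or PR | unstated number of responders | descriptive, unconditional |

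For DCB, the population and the count do not match. As an assumed example, 2 responders and 25 subjects with SD give 2 + 25 = 27 subjects with a DCB, but the trigger sees 2. For DOR and TTR the population matches, but the condition is absent from the protocol. For the Kaplan-Meier variables (DOR and DCB), it also conflicts with SAP section 5.

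**2. How often the condition could withhold the DCB summary**

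Inputs:
- n = 50, the approximate expansion size (SAP section 4).
- True ORR p of 5% to 20%, assumed. The only response rate in the documents is about 10% for aldesleukin (Protocol 2.1), which is background and not a planning rate.
- Minimum number of responders k of 3, 5 or 10, assumed because the SAP gives none.

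With X binomial(n, p), the probability of no summary is P(X ≤ k − 1). For p = 0.10 and k = 3:

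0.9^50 + 50 × 0.1 × 0.9^49 + 1225 × 0.1² × 0.9^48 = 0.0052 + 0.0286 + 0.0779 = 0.112.

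| True ORR | k = 3 | k = 5 | k = 10 |
|---|---|---|---|
| 5% | 54.1% | 89.6% | about 100% |
| 10% | 11.2% | 43.1% | 97.5% |
| 20% | 0.1% | 1.8% | 44.4% |

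If only 40 subjects were evaluable, the 10% row would read 22.3%, 62.9% and 99.5%.

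Now count CR, PR and SD instead, at an assumed combined rate of 30% to 60%. The worst case is 30%: 0.02% for k = 5 and 4.0% for k = 10, and practically zero for k = 3. At 40% the k = 10 figure is 0.08%.

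**3. The DCB clock (optional part)**

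Scans are every 8 weeks ± 7 days from Cycle 1 Day 1 (Protocol 6.4), so the first SD date falls at about week 7 to 9. DCB under the SAP = week of PD − week of first CR, PR or SD assessment.

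- PD at week 16: 16 − 8 = 8 weeks (7 to 9), against 16 from first dose.
- PD at week 24: 24 − 8 = 16 weeks (15 to 17), against 24 from first dose.
- PD at week 24 with the week-8 scan missed or not evaluable: 24 − 16 = 8 weeks, against 24 from first dose.

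DOR starts at first CR or PR in both documents, and TTR runs from first dose in SAP 9.3. Neither is affected by this.

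**The case against.** The strongest reply is that little is lost. Every duration is listed by subject. The clinical benefit rate is still summarised unconditionally with an exact interval (SAP 9.2), so a group with many stable subjects would remain visible. With a handful of responders, Kaplan-Meier quartiles say little that a listing does not. DCB is an SAP addition as far as the readable text shows, in a trial whose analyses are all descriptive, and no visible decision rule uses it. A specific section may also be read as overriding the general rule in SAP section 5.

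Most of this stands, and it limits the importance of the point. It does not explain why a DCB summary should depend on a count that leaves out SD. Nor does it reconcile SAP 9.3 and 9.4 with Protocol 10.5.3 and SAP section 14.

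Three stronger readings are tempting, and the documents do not support them:

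- A reader might infer that the durations will go unreported. They are listed in all cases; only the summaries are conditional.
- A reader might infer that durations in general are understated. DOR and TTR values are not shortened. DCB is shorter only relative to a first-dose origin, which no readable text sets, and its stated origin parallels that of DOR. Parts of the endpoint lists and the text after the DCB definition are redacted, so it cannot be said that time from first dose to progression goes unmeasured.
- A reader might infer that the DCB rule contradicts the protocol. DCB does not appear in the readable protocol, so the departure concerns DOR and TTR only.

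**Conclusion.** The point holds in limited form, as a minor defect in SAP wording. The DCB condition counts the wrong subjects and has no stated minimum. The DOR and TTR conditions are an undeclared departure from Protocol 10.5.3, and for Kaplan-Meier variables the SAP also disagrees with its own section 5.

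The size cannot be fixed, because the minimum is unstated. At an assumed ORR of 10% in 50 subjects, the chance of no DCB summary runs from 11% to 97.5% as the assumed minimum goes from 3 to 10 responders. A count that included SD would nearly always meet the same minimum. The response rates, clinical benefit rates, minimum counts and the example of 2 responders with 25 SD are all assumptions.

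The DCB start date is a matter for explanation, not an error. The redacted censoring table was not judged.

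**What to change.** 1. **DCB (SAP 9.4):** summarise it without reference to ORR. If a minimum is wanted, state it as a number and count the subjects for whom DCB is defined (CR, PR or SD).
2. **DOR and TTR (SAP 9.3 and 9.4):** delete the condition so that both follow Protocol 10.5.3. Where responders are few, report medians as not estimable alongside the listing.
3. **Optional, DCB origin:** give the reason for starting at the first CR, PR or SD assessment, or also report DCB from first dose.

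The cost is SAP wording. No data collection or sample size changes. The only drawback is that some summaries will rest on very few subjects, which the reported counts will show.

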10 SAFETY ANALYSES

All safety analyses will be based on the safety population unless otherwise specified.

10.1 Dose Limiting Toxicity

A dose-limiting toxicity (DLT) is defined as a grade 3 or higher related or possibly related AE occurring within the first cycle of dosing except:

- Grade 3/4 transient lymphopenia < 14 days in duration,
- tumor flare defined as local pain, irritation, or rash localized at sites of known or suspected tumor,
- a transient, reversible \leq grade 3 infusion AE,
- non-clinically significant laboratory abnormalities, or
- fatigue lasting less than 72 hours

Delayed DLTs are AEs that meet the definition of DLT events and occur after Cycle 1. DLTs and delayed DLTs will be summarized separately for each dose cohort. All DLTs and delayed DLTs will be listed by subject.

10.2 Adverse Events

A treatment emergent adverse event (TEAE) is:

- an AE that was not present prior to treatment and occurred after the first dose of NKTR-214 including partial dose or
- a pre-existing condition that was present before first dose of NKTR-214 and worsened after the first dose of NKTR-214 or
- an AE that was present at treatment initiation, but resolved and then reappeared while the subject was on treatment (regardless of intensity of the AE when the treatment was initiated)

In addition, an AE will be considered to be a TEAE if its status cannot be fully determined due to incomplete data. All AEs will be coded by MedDRA using SOC and PT. Only TEAEs will be summarized in the table. All AEs including non-TEAEs will be listed by subject.

An AE is considered to be related to NKTR-214 if the relationship to study treatment is assessed by investigators as possibly related or related. An AE with missing or unknown relationship will be considered to be a related AE.

For each NKTR-214 related TEAE, the duration of TEAEs will be summarized by SOC and PT. The duration of the NKTR-214 related TEAEs will be calculated as:

$$\text{Duration of AE} = \text{AE stop date} - \text{AE start date} + 1.$$

For subjects who have the same NKTR-214 related TEAE multiple times, the duration will be the average of each individual duration. An incomplete start and end date for a NKTR-214 related TEAE will be imputed as specified in Section 6. The duration of AEs will be summarized by SOC and PT.

A TEAE is considered to be a TEAE leading to death if the severity grade is 5 or the outcome is fatal. A TEAE is considered to be a TEAE leading to NKTR-214 discontinuation if the action taken to NKTR-214 is drug withdrawn. A TEAE is considered to be a TEAE leading to NKTR-214 delay, reduction, or interruption if the action taken to NKTR-214 is dose delayed, dose reduced, or dose interruption.

In each summary table, the total number of events and the number and percentage of subjects who have at least one event will be reported. For TEAE summaries by SOC and/or PT, a subject is counted only once within each summary level. For TEAE summary by CTCAE grade, a subject is counted only once using the highest grade.

The following summaries will be provided for AEs:

- TEAEs by SOC and PT,
- TEAEs by PT,
- TEAEs by severity grade, SOC, and PT,
- TEAEs by severity grade, SOC, and PT in cycle 1,
- NKTR-214 related TEAEs SOC and PT,
- NKTR-214 related TEAEs by PT,
- NKTR-214 related TEAEs by severity grade, SOC, and PT,
- Grade \geq 3 TEAEs by SOC and PT,
- NKTR-214 Related Grade \geq 3 TEAEs by SOC and PT,

- Serious adverse event (SAEs) by SOC and PT,
- NKTR-214 Related SAEs by SOC and PT,
- TEAEs leading to NKTR-214 delay, interruption, or reduction by SOC and PT,
- TEAEs leading to NKTR-214 discontinuation by SOC and PT,
- TEAEs leading to death by SOC and PT,

Selected AEs of special interest will be grouped by pooled PTs, which are provided in Appendix 16.2. The number and percentage of subjects for each AEs of special interest will be presented.

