### **8.2 Monitoring AEs**

All AEs will be assessed by the Investigator and recorded on the appropriate eCRF including but not limited to, the following: the event term, the date of onset and resolution, seriousness, severity, relationship to study drug, outcome, treatment of the event, and action taken with the study drug. AEs will be reported starting immediately after the subject has been administered the first dose of study medication through 30 days after the last dose of NKTR-214.

An event occurring after the subject has provided informed consent, but before the first dose of study treatment, will be collected as medical history unless the event is either new and attributed to protocol-mandated procedures by the Investigator OR there is a significant change in the rate

of occurrence or an increase in the severity of the pre-existing condition which is judged to be clinically important and attributed to the protocol-mandated procedures by the Investigator. Under the latter two circumstances, the event will be considered an AE and will be captured as such on the eCRF.

Example 1:

*Thrombophlebitis associated with a blood draw for assessments required prior to dosing per protocol is an event that is related to protocol-mandated procedures. In this scenario, the event of “thrombophlebitis” will be captured as an AE on the eCRF page, and it will be documented as being “unrelated” to study drug as applicable.*

Example 2:

*An ankle sprain following an unexpected fall from a flight of stairs while at home, after the subject has provided informed consent, but before the first dose of study drug, is clearly unrelated to any protocol-mandated procedures and would therefore be captured as medical history in the medical history section of the eCRF.*

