### 8.3 Grading of AEs

The severity of an event and the seriousness are not to be considered synonymous. The severity is grading the intensity of an event. The seriousness of event is based on the subject/event outcome or action criteria. All AEs will be assessed for severity using the NCI-CTCAE version 4.03. If a particular AE is not listed in the NCI-CTCAE, the following criteria will be used:

- Grade 1 = Mild (event results in mild or transient discomfort, not requiring or needing only minimal intervention or treatment; does not limit or interfere with daily activities (e.g., insomnia, mild headache)
- Grade 2 = Moderate (event is sufficiently discomforting so as to limit or interfere with daily activities; may require interventional treatment (e.g., fever requiring antipyretic medication)
- Grade 3 = Severe (event results in significant symptoms that prevents normal daily activities; may require hospitalization or invasive intervention).
- Grade 4 = Life threatening or disabling
- Grade 5 = Death

AEs will be reported with an individual start and stop date for each level of severity.

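### If AE grade levels are held as separate records, SAP 10.2 reports the mean length of a grade step instead of the event's duration and counts one event several times

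*SAP*

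**What the plan says.** - **Recording.** Protocol 8.3 (Grading of AEs): "AEs will be reported with an individual start and stop date for each level of severity". Protocol 8.2 (Monitoring AEs) gives an open-ended list of what is recorded for each AE, including "the event term, the date of onset and resolution, seriousness, severity, relationship to study drug, outcome". The list names no item that links the records of one episode.
- **Duration.** SAP 10.2 (Adverse Events) computes duration as stop date minus start date plus 1. It says: "For each NKTR-214 related TEAE, the duration of TEAEs will be summarized by SOC and PT". Grade is not a classifier in that summary. For more than one occurrence: "For subjects who have the same NKTR-214 related TEAE multiple times, the duration will be the average of each individual duration".
- **Event totals.** SAP 10.2 says of every summary table that "the total number of events and the number and percentage of subjects who have at least one event will be reported".
- **Subject counts.** SAP 10.2 counts a subject once per SOC and PT, and at the worst grade in tables by CTCAE grade.
- **Joining.** SAP section 6 only imputes incomplete dates, and SAP section 14 plans no changes from the protocol. Neither document says how consecutive grade records of one continuous event are combined.

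**The concern.** The recording rule and the averaging rule each make sense alone. Dates by grade allow time at each severity to be derived, and averaging is reasonable for a toxicity that resolves and later recurs. Together, with nothing between them, they can treat one toxicity that rises and falls in grade as several short ones. The averaged figure is then the mean length of a grade step, although the table presents it as the duration of the toxicity. Because the table does not split by grade, it cannot be read as time at each grade either.

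Safety and tolerability are a primary objective, and the protocol synopsis commits to summarizing the duration of toxicities as well as their incidence and grade. Events that escalate and then resolve are shortened most. If grade changes are more common in some dose cohorts than in others, comparisons of duration across cohorts are distorted as well.

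**Working it through.** The plan states no figure to reproduce. The check applies the SAP formula to constructed records; all dates are assumed.

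**One continuous event.** Grade 1 on Days 1–3, Grade 3 on Days 4–7, Grade 1 on Days 8–12.

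- Record durations: 3 − 1 + 1 = 3; 7 − 4 + 1 = 4; 12 − 8 + 1 = 5.
- SAP rule: (3 + 4 + 5)/3 = 4 days, 3 events.
- Episode: 12 − 1 + 1 = 12 days, 1 event.
- If adjoining records share a date (Days 1–3, 3–7, 7–12), the durations are 3, 5 and 6. The SAP rule then gives 14/3 = 4.67 days.

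**Other patterns**

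| Pattern | SAP rule, days | SAP rule, events | Joined, days | Joined, events |
|---|---|---|---|---|
| One 10-day episode, records of 3, 3 and 4 days | 3.33 (4.0 with shared dates) | 3 | 10 | 1 |
| One 14-day episode, two 7-day records | 7.0 (7.5 with shared dates) | 2 | 14 | 1 |
| The 10-day episode above plus a separate 4-day episode | (3+3+4+4)/4 = 3.5 | 4 | (10+4)/2 = 7.0 | 2 |
| Two separate episodes of 6 and 4 days, no grade change | 5.0 | 2 | 5.0 | 2 |

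The last row shows that joining leaves true recurrences alone.

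**Direction.** Let a subject have T days of a toxicity in E episodes, held as R records, with R ≥ E and T ≥ E. The episode mean is T/E.

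- Next-day dates: the SAP rule gives T/R, which is at most T/E.
- Shared boundary dates: it gives (T + R − E)/R. The shortfall is T/E − (T + R − E)/R = (R − E)(T − E)/(RE), which is at least 0.

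Under either dating convention, splitting by grade never lengthens the reported duration.

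**Cohort level.** The documents do not say how often grades change. Assume one episode per subject, equal episode lengths and next-day dates, and let a fraction f of episodes split into k records. Mean duration is then multiplied by (1 − f) + f/k, and the event total by (1 − f) + fk.

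| f | Duration, k = 2 | Events, k = 2 | Duration, k = 3 | Events, k = 3 |
|---|---|---|---|---|
| 10% | 0.95 | 1.10 | 0.93 | 1.20 |
| 25% | 0.875 | 1.25 | 0.83 | 1.50 |
| 50% | 0.75 | 1.50 | 0.67 | 2.00 |

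These are ranges under assumption, not estimates for this trial.

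**The case against.** The strongest objection is that separate records are an inference. Protocol 8.3 asks for separate dates by severity level; it does not say separate AE entries. Protocol 8.2 records onset and resolution, and a change of grade is not a resolution. An eCRF with severity rows under a single AE would satisfy both sections. The SAP wording on multiple occurrences may also have been meant only for true recurrences. This stands as a limit on certainty, but it does not close the gap. If the rows are linked, neither document says so. If the averaging is for recurrences only, the SAP has no rule for grade-level records at all.

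The effect on use is also limited. The analyses are descriptive, and all AEs are listed by subject, so a reader with the listings could rebuild the episodes. The summary table would still be wrong for the affected events.

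Four stronger readings are tempting and are not supported:

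- **Every AE table has inflated event totals.** In the Grade 1–3–1 example, the tables of Grade 3 or higher events contain one record, not three. Tables defined by death, discontinuation, or delay, reduction or interruption select on grade, outcome or action taken, so they need not pick up every step. For AEs of special interest, the SAP describes only the number and percentage of subjects.
- **Duration is always divided by the number of grade steps.** That holds only for one episode with next-day dates. In the working, a three-record episode plus a second episode halves the mean instead of cutting it to a third.
- **All reported durations are biased downward on balance.** Only this mechanism has that direction. SAP section 6 sets a completely missing AE stop date to the date of study discontinuation, which can lengthen durations.
- **DLT classification is affected, for example through the exclusion of** "Grade 3/4 transient lymphopenia < 14 days in duration". SAP 10.1 does not refer to the 10.2 formula or its averaging, and the exclusion names Grades 3 and 4 together. Under protocol 4.1.2.1, escalation is decided when the first three subjects complete Cycle 1, not from the SAP duration table.

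**Conclusion.** The point holds conditionally. If grade levels are held as separate records, SAP 10.2 as written reports the mean length of a grade step for any related toxicity of more than one day that changes grade. It also counts that toxicity more than once in tables not restricted by grade, action taken or outcome. The condition is what the protocol wording implies, but it cannot be confirmed without the eCRF.

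For a single event the error can be large: 4 or 4.67 days against 12. At cohort level it cannot be fixed from the documents. The numbers and percentages of subjects and the worst-grade tables are unaffected, and nothing here bears on DLT determination. This is more than a missing detail, because a stated averaging rule meets a stated recording rule and gives a wrong value for a summary that the synopsis commits to.

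**What to change.** Add to SAP 10.2 that, before durations and event totals are computed:

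1. Records of the same preferred term within a subject that are contiguous or overlapping are joined into one episode. Contiguous means that the next start falls on the same day as, or the day after, the previous stop.
2. Episode duration is last stop − first start + 1, and the episode carries its worst grade.
3. Durations are averaged only across episodes separated by resolution.

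Time at Grade 3 or higher can be reported separately from the grade-level records if wanted. If the eCRF or the programming already links severity rows under one AE, the SAP should say so and state that durations and event totals are taken at the linked level.

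The cost is SAP wording and a short derivation step, with no new data and no protocol change. Reported durations become longer and event totals smaller wherever grade changes occurred. The change is confined to the 10.2 summaries and does not touch the DLT definition.
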